7.6.11 Immune-Mediated Adverse Events

In order to further characterize AEs of special clinical interest analysis of immune-mediated AEs (IMAE) will be conducted. Immune-mediated AEs are specific events (or groups of PTs describing specific events) that include pneumonitis, diarrhea/colitis, hepatitis, nephritis/renal dysfunction, rash, endocrine (adrenal insufficiency, hypothyroidism/thyroiditis, hyperthyroidism, diabetes mellitus, and hypophysitis), and other specific events, considered as potential immune-mediated events by investigator, that meet the definition summarized below:

- those occurring within 100 days of the last dose,
- regardless of causality,
- treated with immune-modulating medication (of note, endocrine Adverse events such as adrenal insufficiency, hypothyroidism/thyroiditis, hyperthyroidism, diabetes mellitus, and hypophysitis are considered IMAEs regardless of immune-modulating medication use, since endocrine drug reactions are often managed without immune-modulating medication).

The list of MedDRA preferred terms used to identify Immune-Mediated adverse events is revisited quarterly and updated accordingly. The preferred terms used for the selection at the time of the database lock by categories will be provided.

IMAEs will be summarized by treatment group for each immune mediated category / PT using the 100-day safety window:

- Overall summary of AEs by worst CTC grade (grade 1, 2, 3, 4, 5, unknown) presented by immune mediate Category / PT. This summary includes all AEs that are qualified for IMAE preferred terms list, without requirement of either usage of immune modulating medications or accounting for immune mediated etiology or immune mediated component.
- Overall summaries of IMAEs by worst CTC grade [(grade 1, 2, 3, 4, 5, unknown) and (any grade, grade 3-4, grade 5)] where immune modulating medication was initiated presented by Category / PT.
- Overall summaries of endocrine IMAEs by worst CTC grade [(grade 1, 2, 3, 4, 5, unknown) and (any grade, grade 3-4, grade 5)] presented by Category / PT.
- Overall summaries of serious IMAEs by worst CTC grade [(grade 1, 2, 3, 4, 5, unknown) and (any grade, grade 3-4, grade 5)] where immune modulating medication was initiated presented by Category / PT.
- Overall summaries of endocrine serious IMAEs by worst CTC grade [(grade 1, 2, 3, 4, 5, unknown) and (any grade, grade 3-4, grade 5)] presented by Category / PT.
- Overall summaries of IMAEs leading to discontinuation by worst CTC grade [(grade 1, 2, 3, 4, 5, unknown) and (any grade, grade 3-4, grade 5)] where immune modulating medication was initiated presented by Category / PT.
- Overall summaries of endocrine IMAEs leading to discontinuation by worst CTC grade [(grade 1, 2, 3, 4, 5, unknown) and (any grade, grade 3-4, grade 5)] presented by Category / PT.
- Overall summaries of IMAEs leading to dose delay or reduction by worst CTC grade [(grade 1, 2, 3, 4, 5, unknown) and (any grade, grade 3-4, grade 5)] where immune modulating medication was initiated presented by Category / PT
- Overall summaries of endocrine IMAEs leading to dose delay or reduction by worst CTC grade [(grade 1, 2, 3, 4, 5, unknown) and (any grade, grade 3-4, grade 5)] presented by Category / PT.
- Summaries of time to onset and time to resolution of IMAEs where immune modulating medication was initiated presented by Category.
- Summaries of time to onset and time to resolution of endocrine IMAEs presented by Category.

By-subject listing of IMAEs and listing of IMAE definition will be provided. By-subject listings of time to resolution for longest IMAEs cluster (any grade and grade 3-5 in separate summaries) will also be provided.

In addition, for all nivolumab treated subjects who experienced at least one immune-mediated adverse event, the following data presentation will be provided:

- Summary of subjects who were re-challenged with nivolumab by immune-mediated adverse event category, with extended follow-up

- Summary of subjects who were re-challenged with nivolumab or ipilimumab by immune-mediated adverse event category with extended follow-up

For these, re-challenge is considered to have occurred when last nivolumab and/or ipilimumab infusion was administered after the onset of an IMAE.

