4.5.2 Dose Delay Criteria

Dose delay criteria apply for all drug-related adverse events (regardless of whether or not the event is attributed to nivolumab, ipilimumab, or both). All study drugs must be delayed until treatment can resume. See [Section 4.5.4](#).

Ipilimumab and / or nivolumab administration should be delayed for the following:

- Any Grade ≥ 2 non-skin, drug-related adverse event, with the following exceptions:
 - Grade 2 drug-related fatigue or laboratory abnormalities do not require a treatment delay
- Any Grade 3 skin, drug-related adverse event
- Any Grade 3 drug-related laboratory abnormality, with the following exceptions for lymphopenia, AST, ALT, or total bilirubin or asymptomatic amylase or lipase:
 - Grade 3 lymphopenia does not require dose delay
 - If a subject has a baseline AST, ALT, or total bilirubin that is within normal limits, delay dosing for drug-related Grade ≥ 2 toxicity
 - If a subject has baseline AST, ALT, or total bilirubin within the Grade 1 toxicity range, delay dosing for drug-related Grade ≥ 3 toxicity
 - Any Grade ≥ 3 drug-related amylase or lipase abnormality that is not associated with symptoms or clinical manifestations of pancreatitis does not require dose delay. The BMS Medical Monitor should be consulted for such Grade ≥ 3 amylase or lipase abnormalities.
- Any adverse event, laboratory abnormality, or intercurrent illness which, in the judgment of the investigator, warrants delaying the dose of study medication.

Subjects who require delay of ipilimumab or nivolumab should be re-evaluated weekly or more frequently if clinically indicated and resume ipilimumab or nivolumab dosing when re-treatment criteria are met.

Tumor assessments should continue as per protocol even if dosing is delayed.

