4.5.5 Discontinuation of Study Drug

Treatment should be permanently discontinued for the following:

- Any Grade 2 drug-related uveitis or eye pain or blurred vision that does not respond to topical therapy and does not improve to Grade 1 severity within the re-treatment period OR requires systemic treatment
- Any Grade 3 non-skin, drug-related adverse event lasting > 7 days, with the following exceptions for laboratory abnormalities, drug-related uveitis, pneumonitis, bronchospasm, hypersensitivity reactions, infusion reactions, and endocrinopathies:
 - Grade 3 drug-related uveitis, pneumonitis, bronchospasm, hypersensitivity reaction, or infusion reaction of any duration requires discontinuation
 - Grade 3 drug-related endocrinopathies adequately controlled with only physiologic hormone replacement do not require discontinuation
 - Grade 3 drug-related laboratory abnormalities do not require treatment discontinuation except:
 - ◆ Grade 3 drug-related thrombocytopenia > 7 days or associated with bleeding requires discontinuation
- Any drug-related liver function test (LFT) abnormality that meets the following criteria require discontinuation:
 - AST or ALT > 8 x ULN

- Total bilirubin > 5 x ULN
- Concurrent AST or ALT > 3 x ULN and total bilirubin > 2 x ULN
- Any Grade 4 drug-related adverse event or laboratory abnormality, except for the following events which do not require discontinuation:
 - Grade 4 neutropenia ≤ 7 days
 - Grade 4 lymphopenia or leukopenia
 - Isolated Grade 4 amylase or lipase abnormalities that are not associated with symptoms or clinical manifestations of pancreatitis. The BMS Medical Monitor should be consulted for Grade 4 amylase or lipase abnormalities.
 - Isolated Grade 4 electrolyte imbalances/abnormalities that are not associated with clinical sequelae and are corrected with supplementation/appropriate management within 72 hours of their onset
- Any event that leads to delay in dosing lasting > 6 weeks from the previous dose requires discontinuation, with the following exceptions:

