7.1 General Methods

Descriptive summaries will be presented for continuous variables using number of subjects (N), mean, standard deviation, median, minimum and maximum. Descriptive summaries for categorical variables will utilize counts and percentages. Corresponding by-subject listings will also be created for appropriate populations.

Time to event distributions (i.e. progression free survival, overall survival, time to response, and duration of response) will be estimated using Kaplan Meier techniques. When appropriate, the median along with 95% CI will be estimated based on Brookmeyer and Crowley methodology¹ (using log-log transformation for constructing the confidence intervals). Rates at fixed timepoints (e.g. OS at 12 months) will be derived from the Kaplan Meier estimate along with their corresponding log-log transformed 95% confidence intervals. Confidence intervals for binomial proportions will be derived using the Clopper-Pearson method.

AEs and medical history will be coded according to the most recent Medical Dictionary for Regulatory Activities (MedDRA). Previous and concomitant medications will be coded using the World Health Organization (WHO) Drug Dictionary.

7.1.1 **Adverse Events, Serious Adverse Events, Multiple events and Select Adverse Events**

Drug-related AEs are those events with relationship to study drug “Related”, as recorded on the CRF. If the relationship to study drug is missing, the AE will be considered as drug-related.

Serious adverse events consist of AEs deemed serious by the Investigator and flagged accordingly in the CRF and clinical database.

Adverse events leading to study drug discontinuation are AEs with action taken = “Drug was discontinued”.

Adverse events leading to dose delay are AEs with action taken = “Dose was delayed”.

Adverse events leading to dose reduction are AEs with action taken = “Dose was reduced”.

Adverse events will be coded using the Medical Dictionary for Regulatory Activities (MedDRA), and the most recent version of the dictionary at the time of the database lock will be used. Adverse events results will be graded for severity using NCI Common Terminology Criteria for Adverse Events (CTCAE) Version 4.0 criteria.

In the AE summary tables, unless otherwise specified, subjects will be counted only once at the Preferred Term (PT), only once at the System Organ Class (SOC), and only once at subject level

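### SAP 7.6.11 counts any infusion after the onset of an immune-mediated AE as re-challenge, so its tables merge subjects who never interrupted dosing with those who stopped and restarted, and can only overstate restarts

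*SAP*

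**What the plan says.** SAP 7.6.11 plans, "for all nivolumab treated subjects who experienced at least one immune-mediated adverse event", two summaries. The first is a "Summary of subjects who were re-challenged with nivolumab by immune-mediated adverse event category, with extended follow-up"; the second is the same for nivolumab or ipilimumab. One sentence defines the term for both: "re-challenge is considered to have occurred when last nivolumab and/or ipilimumab infusion was administered after the onset of an IMAE".

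The same section sets what counts as an IMAE. Events within 100 days of the last dose qualify "regardless of causality". Non-endocrine events must have been treated with immune-modulating medication. Endocrine events "are considered IMAEs regardless of immune-modulating medication use".

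Protocol 4.5.2 lists when dosing should be delayed. The specific triggers concern drug-related events: Grade 2 or higher for non-skin events, with exceptions that include Grade 2 fatigue and Grade 2 laboratory abnormalities; for skin, "Any Grade 3 skin, drug-related adverse event"; and Grade 3 laboratory abnormalities, with exceptions. A last item lets the investigator delay for any event.

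The SAP defines interruption elsewhere. In 7.1.1, "Adverse events leading to dose delay are AEs with action taken" recorded as a delay, and events leading to discontinuation are identified in the same way. In 7.4.2.1, a dose is actually delayed when it is more than 3 days late, with the reason taken from the CRF dosing pages. Neither definition enters the re-challenge rule.

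**The concern.** Re-challenge is naturally read as giving a drug again after it was stopped or held for a reaction. The rule compares only two dates, IMAE onset and last infusion. It therefore also counts subjects who were never taken off drug, and a subject who received one more scheduled dose shortly after onset and was then stopped for good because of that event.

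The two groups answer different questions. Subjects dosed through an event tend to be those whose event called for no delay, because it was mild or was not attributed to drug. Subjects held and restarted had an event serious enough to interrupt dosing. If the groups are merged, a reader cannot tell how many subjects restarted after an interruption, which is what the table title suggests it reports.

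**Working it through.** The plan states no figure to reproduce, so the check is of the definition.

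**Step 1: what the rule flags.** The last infusion falls after onset exactly when at least one infusion falls after onset. The rule is therefore equivalent to any infusion after IMAE onset.

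**Step 2: a subject with no delay.** Take the schedule in Protocol 4.5: four combination doses on days 0, 21, 42 and 63, then nivolumab every 14 days from day 84. Suppose every dose is given on time. An onset on any day from day 1 to the day before the last dose is flagged:

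| Doses received | Last dose (day) | Onset days flagged | Delays over 3 days |
|---|---|---|---|
| 4 | 63 | 62 of 62 | 0 |
| 10 | 84 + 5 × 14 = 154 | 153 of 153 | 0 |
| 51 | 84 + 46 × 14 = 728 | 727 of 727 | 0 |

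**Step 3: can such subjects occur under this protocol?** Setting the IMAE definition beside the delay triggers in Protocol 4.5.2 gives the main routes to being flagged without interruption:

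- Grade 1 endocrine events: IMAEs without any medication requirement, and below the Grade 2 trigger.
- Skin events below Grade 3 that were given immune-modulating medication: IMAEs, but below the skin trigger.
- Events judged unrelated to drug: IMAEs whatever the causality, but outside the drug-related triggers.
- Any event with a scheduled dose shortly after onset and no later dose.

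In each case the investigator may still choose to delay, so these routes are open but not certain to be taken.

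**Step 4: direction.** A restart is an infusion after an interruption that itself follows onset. Every restart therefore satisfies the rule and none is missed. As a count of restarts, the error can only be upward.

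**Step 5: size.** Let N subjects be flagged and let a share u of them have had no interruption. Restarts number N(1-u), so the overstatement factor is N / [N(1-u)] = 1/(1-u). The documents give neither N nor u. With an assumed u from 0 to 0.5 and an assumed N of 40:

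| u | Factor 1/(1-u) | Restarts among 40 flagged |
|---|---|---|
| 0 | 1.00 | 40 |
| 0.1 | 1.11 | 36 |
| 0.2 | 1.25 | 32 |
| 0.3 | 1.43 | 28 |
| 0.4 | 1.67 | 24 |
| 0.5 | 2.00 | 20 |

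**The case against.** The best defence is that this is a stated convention. The SAP says what it means by re-challenge, attaches no test or decision to the tables, and nowhere promises evidence on restarting treatment. That stands, and it makes this a matter of labelling and interpretation.

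A second defence is that the missing information is planned elsewhere: tables of IMAEs leading to dose delay and to discontinuation, by-subject IMAE and dosing listings, and a summary of delays with reasons. A reader with the listings could separate many of the subjects by hand. The delay and discontinuation tables alone do not settle it, because they show that dosing was held or stopped and not whether drug was given again. The SAP also refers to a core safety SAP and a Data Presentation Plan, which are not available here and might add detail.

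Third, the uninterrupted group is limited. Non-endocrine IMAEs need immune-modulating medication, and drug-related non-skin events of Grade 2 or higher generally call for delay. This also stands.

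Two stronger readings are tempting but unsupported:

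- A reader might infer from Protocol 4.5.5 that Grade 3 endocrine events are dosed through, since "Grade 3 drug-related endocrinopathies adequately controlled with only physiologic hormone replacement do not require discontinuation". That sentence concerns permanent discontinuation. Such events still meet the Grade 2 or higher delay trigger in 4.5.2, and 4.5.4 sets conditions for resuming, so they describe interruption followed by restart.
- A reader might infer that the and/or wording inflates the nivolumab table with ipilimumab infusions. Ipilimumab is scheduled only on days when nivolumab is also given, and 4.5.2 delays all study drugs together, so the effect should be small.

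**Conclusion.** The point holds as a minor one. The two re-challenge tables in SAP 7.6.11 pool dosing continued through an IMAE with dosing resumed after an interruption, and as a measure of restarting they can only overstate.

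A reader might go further and infer that the overstatement is large. The documents do not support that: they give no count of IMAEs, interruptions or restarts, and the excess is zero if every flagged subject was interrupted. The factor of 1.0 to 2.0 rests wholly on the assumed range of u from 0 to 0.5.

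The conclusion rests on two things: no available section adds an interruption condition, and readers will take re-challenge to mean restarting. The primary endpoint and the other planned safety tables are unaffected.

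**What to change.** In both tables, split the present count into two rows within each IMAE category:

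1. **Re-challenged:** an infusion of the named drug after an interruption recorded for that IMAE. Interruption means an AE action taken of dose delayed or drug discontinued, or a dose delay as defined in SAP 7.4.2.1 with that AE as the reason.
2. **Study drug given after IMAE onset, no recorded interruption.**

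Only row 1 carries the label re-challenge. The sum of the rows is the current total, so comparison with summaries that use the broader definition is kept.

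An infusion after the event's resolution date should not be an alternative route into row 1. An event that starts on day 5, resolves on day 15 and is followed by the on-time day 21 dose would qualify although dosing was never interrupted.

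The cost is one revised derivation and one extra row per table. The SAP places action taken and reason for delay on the CRF. It does not say whether the delay reason names the individual AE, so that link should be confirmed before programming. No dosing rule changes.

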7.6.12 Clinical laboratory evaluations

7.6.12.1 Hematology

The following will be summarized for all treated subjects, and by cohorts and by SRT status, as worst CTC grade on-treatment per subject and as shift table of worst on-treatment CTC grade compared to baseline CTC grade per subject: hemoglobin, platelets, white blood counts, absolute neutrophils count and lymphocyte count.

The analyses will be conducted using the 30-day safety window and repeated using the 100-day safety window.

A by-subject listing of these laboratory parameters will be provided.

7.6.12.2 Serum Chemistry

The following will be summarized for all treated subjects, and by cohorts and by SRT status, as worst CTC grade on-treatment per subject and as shift table of worst on-treatment CTC grade compared to baseline CTC grade per subject: ALT, AST, alkaline phosphatase, total bilirubin, creatinine, amylase and lipase.

The analyses will be conducted using the 30-day safety window and repeated using the 100-day safety window.

A by-subject listing of these laboratory parameters will be provided.

7.6.12.3 Electrolytes

The following will be summarized by treatment group as worst CTC grade on-treatment per subject and as shift table of worst on-treatment CTC grade compared to baseline CTC grade per subject: sodium (high and low), potassium (high and low), calcium (high and low), magnesium (high and low).

The analyses will be conducted using the 30-day safety window and repeated using the 100-day safety window.

A by-subject listing of these laboratory parameters will be provided.

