Procedure	Cycle 1 and Cycle 2 (Cycle = 6 weeks)						Notes • Tumor assessment should be continued as per protocol even if dosing is delayed
	Day 1 Week 1	Day 1 Week 2	Day 1 Week 3	Day 1 Week 4	Day 1 Week 5	Day 1 Week 6	
Safety Assessments							
Targeted Physical Examination Cycle 1	X	X	X	X	X	X	Cycle 1: Weekly for first 6 weeks: conducted by study physician; Within 72 hours prior to dosing on Weeks 1 and 4.
Cycle 2	X			X			Cycle 2: Weeks 1 and 4: conducted by study physician within 72 hours prior to dosing.
Phone assessment with study medical staff: Cycle 2 only.		X	X		X	X	Cycle 2: Weeks 2,3,5,6 * Phone assessment with study medical staff required
Vital Signs and Oxygen Saturation Cycle 1	X	X	X	X	X	X	Including BP, HR, temperature, and oxygen saturation by pulse oximetry. Pulse oximetry at rest and after exertion prior to dosing. Cycle 1: Weekly for first 6 weeks.
Cycle 2	X			X			Cycle 2: Weeks 1 and 4 only
Physical Measurements (including performance status) Cycle 1	X	X	X	X	X	X	Weight and ECOG status within 72 hours prior to dosing. Cycle 1: Weekly for first 6 weeks.
Cycle 2	X			X			Cycle 2: Weeks 1 and 4 only
Adverse Events Assessment	Continuously						
	■	■	■	■	■	■	
	■	■	■	■	■	■	

Table 5.1-2: On-study Assessments Cycles 1 and 2 Only (CA209204)							
Procedure	Cycle 1 and Cycle 2 (Cycle = 6 weeks)						Notes • Tumor assessment should be continued as per protocol even if dosing is delayed
	Day 1 Week 1	Day 1 Week 2	Day 1 Week 3	Day 1 Week 4	Day 1 Week 5	Day 1 Week 6	
Laboratory Tests	X			X			Within 72 hrs prior to dosing to include CBC w/differential, LFTs, BUN or serum urea level, creatinine, Ca, Mg, Na, K, Cl, LDH, Glucose, amylase, lipase, TSH (with reflexive Free T4 and Free T3)
Pregnancy Test (WOCBP Only)	X			X			Within 24 hours prior to administration of study drug. Serum or Urine
[REDACTED]	[REDACTED]						[REDACTED]
[REDACTED]							[REDACTED]
[REDACTED]			[REDACTED]				[REDACTED]
[REDACTED]			[REDACTED]				[REDACTED]
[REDACTED]			[REDACTED]				[REDACTED]
[REDACTED]			[REDACTED]				[REDACTED]

Table 5.1-2: On-study Assessments Cycles 1 and 2 Only (CA209204)							
Procedure	Cycle 1 and Cycle 2 (Cycle = 6 weeks)						Notes • Tumor assessment should be continued as per protocol even if dosing is delayed
	Day 1 Week 1	Day 1 Week 2	Day 1 Week 3	Day 1 Week 4	Day 1 Week 5	Day 1 Week 6	
Efficacy Assessments							

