Adverse Events Assessment	X	X	All SAEs must be collected that occur within 100 days of the last dose of study drug(s). All nonserious adverse events (not only those deemed to be treatment-related) should be collected for a minimum of 100 days following discontinuation of study treatment. Every adverse event must be assessed by the investigator with regard to whether it is considered immune-mediated. For events which are potentially immune-mediated, additional information will be collected on the subject's case report form.
Laboratory Tests	X		Perform Lab tests for Follow-up Visit 1 and repeat at Follow-up Visit 2, if any study drug toxicity persists. CBC w/differential, LFTs, BUN or serum urea level, creatinine, glucose, amylase, lipase, TSH (with reflexive Free T4 and Free T3).
Pregnancy Test (WOCBP Only)	X		Serum or urine
████████████████████	█		████████████████████
Document any current treatment regimen	X	X	To include immuno-therapy, chemotherapy, targeted therapy, radiotherapy, surgery, and all interventions to treat metastatic melanoma.
Survival Status		X	
Subject Status	X	X	Every 3 months, may be accomplished by visit or phone contact, to include subsequent anti-cancer therapy
████████████████████	█		████████████████████

Table 5.1-4: Follow-up Assessments (CA209204)			
Procedure	Follow-Up^a Visits 1 and 2	Survival^b Follow-up Visits	Notes Follow up is 3 years from start of treatment.
Efficacy Assessments			
Tumor Assessments	X		
Only for subjects who have not progressed on study therapy or who have discontinued study treatment for reasons other than documented disease progression.
 
Section 5.4
 
CT/MRI of chest, abdomen, pelvis and brain (MRI)
 
FIRST tumor assessment should first be performed at 6 weeks (± 7 days) from first dose date.
 
SUBSEQUENT tumor assessments should occur every 6 weeks (± 7 days) up to first 12 months (week 48), then every 12 weeks (± 7 days) until documented disease progression.

██████████	█		
████████████████████	█	█	████████████████████

^a Follow-up Visit 1 = 30 days from the last dose +/- 7 days or coincide with the date of discontinuation (+/- 7 days) if date of discontinuation is greater than 37 days after last dose, Follow-up visit 2 = 84 days (+/- 7 days) from follow-up visit 1

^b Survival visits = every 3 months from Follow-up Visit 2 +/- 7 days

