6 STUDY PERIODS, TREATMENT REGIMENS AND POPULATIONS FOR ANALYSES

6.1 Study Periods

6.1.1 *Baseline period*

Baseline evaluations or events will be defined as the last non-missing evaluation or event that occurs before the date and time of the first dose of study treatment.

In cases where the time (onset time of event or evaluation time and dosing time) is missing or not collected, the following definitions will apply:

- Baseline evaluations (laboratory tests and vital signs) will be defined as evaluations with a date on or prior to the day of first dose of study treatment in part I.

If there are multiple valid pre-treatment assessments, the assessment that is closest to the day (and time if collected) of the first dose of study treatment in part I will be used as the baseline in the analyses.

- Pre-treatment AEs will be defined as AEs with an onset date prior to but not including the day of the first dose of study treatment in part I.

If there are multiple valid pre-treatment assessments, the assessment that is closest to the day (and time if collected) of the first dose of study treatment will be used as the baseline in the analyses. If multiple assessments are collected at the same date (and time if collected), the assessment with the latest database entry date (and time if collected) will be considered as baseline.

If more than one tumor biopsy specimen is available, baseline PD-L1 expression will be determined from the most recently collected specimen (prior to first dose of study treatment) with a measurable result. If all specimens for a given subject are either indeterminate or unknown, then the PD-L1 expression will be considered indeterminate as long as at least one specimen is indeterminate. Otherwise, PD-L1 expression will be considered unknown.

6.1.2 *On study period*

On-study evaluations (laboratory tests and vital signs) will be defined as evaluations taken after the day (and time, if collected and not missing) of first dose of study treatment. For subjects who are off study treatment, evaluations should be within 100 days of the last dose of study treatment.

On-study AEs will be defined as AEs with an onset date-time on or after the date-time of the first dose of study treatment in part I (or with an onset date on or after the day of first dose of study treatment if time is not collected or is missing). For subjects who are off study treatment, AEs will

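### SAP 7.6.12.3 reports sodium, potassium, calcium and magnesium to 30 and 100 days after the last dose, but no follow-up visit in protocol Table 5.1-4 schedules any of the four

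*SAP*

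**What the plan says.** SAP 7.6.12.3 covers "sodium (high and low), potassium (high and low), calcium (high and low), magnesium (high and low"), each as worst on-treatment CTC grade and as a shift from baseline. It then adds: "The analyses will be conducted using the 30-day safety window and repeated using the 100-day safety window". SAP 6.1.2 sets the outer limit for laboratory values: "For subjects who are off study treatment, evaluations should be within 100 days of the last dose of study treatment".

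Protocol Table 5.1-2 (Cycles 1 and 2, Weeks 1 and 4) gives the on-study panel: "Within 72 hrs prior to dosing to include CBC w/differential, LFTs, BUN or serum urea level, creatinine, Ca, Mg, Na, K, Cl, LDH", followed by glucose, amylase, lipase and TSH. Table 5.1-3 (Cycle 3 onward) has the same panel at Weeks 1 and 5.

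Protocol Table 5.1-4 gives the follow-up panel: "CBC w/differential, LFTs, BUN or serum urea level, creatinine, glucose, amylase, lipase, TSH (with reflexive Free T4 and Free T3"). Its timing rules are "Follow-up Visit 1 = 30 days from the last dose +/- 7 days" (or at discontinuation, if that is more than 37 days after the last dose) and "Follow-up visit 2 = 84 days (+/- 7 days) from follow-up visit 1". The instruction for the tests is: "Perform Lab tests for Follow-up Visit 1 and repeat at Follow-up Visit 2, if any study drug toxicity persists".

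Protocol 5.3.7 takes serum chemistry from Tables 5.1-1 to 5.1-4 and names no other source.

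**The concern.** A table labelled as covering 100 days after the last dose leads the reader to expect a planned measurement in that period. For electrolytes there is none at any follow-up visit. The neighbouring haematology and serum chemistry tables (SAP 7.6.12.1 and 7.6.12.2) use the same windows, but the follow-up panel covers their parameters through the blood count, liver tests, creatinine, amylase and lipase. Electrolytes are the exception among the three.

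Scheduled electrolyte draws are tied to planned dosing, so whether a subject has a value after the last dose depends on how and when treatment stopped, including stopping for toxicity. The protocol treats these abnormalities as consequential: its discontinuation rules in 4.5.5 have a separate provision for isolated Grade 4 electrolyte abnormalities. At stake is whether the post-treatment electrolyte tables can be read as evidence of little late toxicity, or only of little late testing.

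**Working it through.** The plan states no figure for this point, so there is none to reproduce. The check compares the panels and then does day arithmetic.

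**1. Panels.** On-study panel (Tables 5.1-2 and 5.1-3) minus follow-up panel (Table 5.1-4) = Ca, Cl, K, LDH, Mg, Na. Of the four electrolytes in SAP 7.6.12.3, 0 are in the follow-up panel.

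**2. Follow-up visits, in days after the last dose.**
- Visit 1: 30 − 7 = 23 to 30 + 7 = 37. Days 23 to 30 fall in the 30-day window; all of days 23 to 37 fall in the 100-day window.
- Visit 2: earliest 23 + 84 − 7 = 100; latest 37 + 84 + 7 = 128; nominal 30 + 84 = 114. It touches the 100-day window only at its last day, and its tests are conditional on persisting toxicity. Where Visit 1 moves to a later discontinuation date, Visit 2 moves later too.

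**3. Electrolyte values that can still fall after the last dose.**
- *Panel drawn for a dose then withheld.* Draws are within 72 hours before dosing, doses may be given up to 2 days late, and results are reviewed before the dose (protocol 5.3.7). Induction, 21-day gap: 21 − 3 = 18 to 21 + 2 = 23. Maintenance, next laboratory visit 14 days on: 11 to 16. Maintenance, last dose at Week 1 and next laboratory visit at Week 5 (28 days): 25 to 30. All lie inside both windows.
- *Dose-delay visits.* Protocol 4.5.5 continues laboratory studies at least every 6 weeks during delays over 6 weeks, so by about days 42 and 84. These are inside the 100-day window and can lie outside the 30-day one. The section does not name the analytes; I assume the on-study panel.
- *Unscheduled tests* as clinically indicated (protocol 5.3.1). The same section warns that some assessments may not be captured in the eCRF.

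The scheduled sources that could make the 100-day table differ from the 30-day one are therefore confined to subjects in a long dose delay.

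**4. Count for early stoppers.** Each induction draw precedes a dose and the first is the baseline. A subject who receives k doses and attends no further dosing visit has k − 1 scheduled post-baseline sets: 0 for k = 1, 1 for k = 2. If the next planned visit is attended and the dose withheld, the count is k. So k − 1 is a minimum.

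**5. Direction and size.** Worst grade is a maximum over available values, so losing a value cannot raise it. As an illustration only, let q be the share of the 110 planned subjects whose worst electrolyte grade arises after their last scheduled draw, and u the share of those caught by unscheduled tests. Both are assumptions. Subjects under-graded = 110 × q × (1 − u):

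| q | u = 75% | u = 50% | u = 0 |
|---|---|---|---|
| 0 | 0 | 0 | 0 |
| 2% | 0.6 | 1.1 | 2.2 |
| 5% | 1.4 | 2.8 | 5.5 |
| 10% | 2.8 | 5.5 | 11.0 |

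Nothing in the documents picks a row or a column.

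**The case against.** The strongest reply is that both tables include every on-treatment value. SAP 6.1.2 counts laboratory values from after the first dose, and the 30- and 100-day windows only add a tail. Panels drawn before dose 2 and later are all in. A reader might infer from Table 5.1-4 that the tables hold no scheduled value after dosing, or that a subject stopped after one dose has no scheduled post-baseline electrolyte. The documents do not support either: step 3 shows that a panel drawn for a withheld dose falls inside both windows, and this is a likely situation for a subject stopped for toxicity at a dosing visit. This part of the reply stands.

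It is also fair that known laboratory toxicities are followed after treatment (protocol 5.3.1), and that clinically significant results are recorded as adverse events (protocol 6.3), which have their own 30- and 100-day tables. These safeguards reduce the clinical risk. They do not fill a worst-grade or shift table, and they favour subjects in whom a problem is already suspected.

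Thin coverage late in the 100-day window is not peculiar to electrolytes, since Visit 2 is late and conditional for every analyte. What is peculiar is the absence of even the unconditional Visit 1 value.

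Finally, SAP 7.6.12.3 states no denominator, and SAP section 8 refers safety conventions to a core safety SAP that is not among the documents. An evaluable-subject denominator may already apply.

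**Conclusion.** The mismatch is real: the SAP promises 30- and 100-day electrolyte tables, and no follow-up visit schedules the analytes. Post-treatment ascertainment is incomplete and depends on how treatment ended, and the 100-day table will be close to a repeat of the 30-day one.

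A reader might go further and conclude that the tables understate electrolyte toxicity by a known or large amount. The documents do not show that. The loss for an individual subject can only be downward, but its frequency is unknown; the 0 to 11 subjects in the illustration reflect assumed inputs only. At group level, the proportion abnormal among those tested could even rise if testing is driven by symptoms.

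This is a cheap improvement to a descriptive safety table. It touches no efficacy endpoint or test. It rests on reading the follow-up list in Table 5.1-4 as complete.

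**What to change.** Reconcile SAP 7.6.12.3 with protocol Table 5.1-4. The preferred change is to add Na, K, Ca and Mg to the chemistry sample already drawn at Follow-up Visit 1. Each subject who attends then has one post-treatment value, usually on days 23 to 37; it enters the 30-day table only if drawn by day 30. The cost is one protocol table line and four assays, with no extra visit or blood draw. Adding them at Visit 2 would contribute almost nothing to the 100-day table.

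If collection can no longer change (SAP version 2.3 is dated 3 December 2020), amend the SAP wording only:
- drop the 100-day electrolyte repeat, or footnote that no follow-up visit schedules these analytes;
- use subjects with at least one post-baseline value as the denominator;
- report how many subjects have any electrolyte value after the last dose.

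That costs a few lines of text and one extra count per table.
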